### 3.4 Exploratory Endpoints

The following exploratory criteria will be evaluated:

- The change from baseline in IgE and IgG4 specific to peanut protein components at 3, 6 and 12 months for both DBV712 groups versus the placebo group;
- The change from baseline in total IgE at 3, 6 and 12 months for both DBV712 groups versus the placebo group;
- Enumeration and characterization of reactions triggered by accidental consumption of peanut during the study and analysis of "risk-taking behavior" of parents' subjects (voluntary peanut consumption) during the study;

CONFIDENTIEL / Ne pas diffuser sans autorisation de DBV

CONFIDENTIAL / Do not distribute without DBV authorization

	Statistical Analysis Plan	
	EPITOPE (V712-304) – Statistical Analysis Plan	
	Référence du Document /Document Reference : CCI [REDACTED]	Page : 16 / 74

CCI [REDACTED]

- Sensitization status to other allergens (e.g., cow's milk, egg, house dust mites, grass pollen) and their evolution over the study period;
- SCORAD evolution over time;
- [REDACTED]
- Quality of Life analysis using the EQ-5D-5L;
- Basophil activation test (BAT) analyses (US eligible sites only).

## 4 ANALYSES SETS

### 4.1 Enrolled Set (ENRL)

The Enrolled set consists of subjects whose parents/guardians have signed informed consent in the Part B of the study.

### 4.2 Full Analysis Set (FAS)

The FAS will include all subjects who are randomized in Part B of the study.

All analyses describing the FAS will be performed according to the randomized treatments (i.e. treatments allocated by randomization).

### 4.3 Per-protocol Set (PP)

This PP set will include all subjects from the FAS who do not have major protocol deviations that may affect the primary efficacy endpoints. The deviations to consider are listed more exhaustively in section 5.3.2 and in Appendix 8.1 and will be reviewed during the Blinded Data Review Meeting (BDRM). This population will be analyzed according to study treatment that was actually received by the subjects. In case the wrong IMP is taken, the subject will be analyzed according to the IMP received for the longest period of time.

The PP set will be used to evaluate the robustness of the primary and secondary efficacy analyses.

### 4.4 Safety Set (SAF)

The Safety population will be comprised of all subjects from the FAS who have received at least 1 dose of IMP in Part B. This population will be used to assess comparative safety information. In case the wrong IMP is dispensed, the subject will be analyzed according to the IMP received for the longest period of time.

	Statistical Analysis Plan	
	EPITOPE (V712-304) – Statistical Analysis Plan	
	Référence du Document /Document Reference : CCI	Page : 17 / 74

CCI

### Analyses sets summary

The following table lists the analyses performed on each dataset:

	ENRL	FAS	PP	SAF
Screen failures	x			
Subject disposition		X	x	
Demographic variables and Baseline Characteristics		X	(x)	
Medical history				x
Disease history				x
Study duration / Exposure / Compliance				x
Primary efficacy analyses		X	x	
Secondary efficacy analyses		X	x	
Other efficacy analyses		X		
Safety analyses				x
Exploratory analyses		X		
(x) Only if PP Set is more than 10% less than FAS				

## 5 STATISTICAL METHODOLOGY

### 5.1 General considerations

The following conventions will be used when presenting summary statistics and analyzing continuous study data:

- Continuous data will be summarized in terms of number of subjects or observations with non-missing data (n), mean, standard deviation (SD), first quartile (Q1), median, third quartile (Q3), minimum (min) and maximum (max), unless otherwise stated.
- For data not normally distributed, a log transformation will be implemented before analysis.
- Compared to the number of decimals recorded for the raw data in the database, the statistics will be reported with the following number of decimals, unless otherwise specified:
  - Minimum and maximum: same number
  - Mean, median, Q1, Q3: one extra decimal
  - Standard deviation: two extra decimals.
- For any parameter at a specific visit or timepoint:
  - Change from Baseline will be calculated as the value of that parameter at that visit minus the Baseline value of that parameter

CONFIDENTIEL / Ne pas diffuser sans autorisation de DBV

CONFIDENTIAL / Do not distribute without DBV authorization

	Statistical Analysis Plan	
	EPITOPÉ (V712-304) – Statistical Analysis Plan	
	Référence du Document /Document Reference : CCI	Page : 18 / 74

CCI

- Relative change from Baseline will be calculated as the value of that parameter at that visit minus the Baseline value of that parameter divided by the Baseline value of that parameter multiplied by 100.
- For laboratory parameters, values below a detection limit or above a specific value (e.g. <0.35 kU/L or >100 kU/L) will be considered as equal to that limit/value (e.g. =0.35 or 100) in the statistical analyses (except in listing where the reported value will be presented).

In case of change of detection limit during the course of the study (e.g. from <0.35 kU/L to <0.1 kU/L), all values lower than the highest limit value will be imputed to this threshold (e.g. all values lower than 0.35 kU/L will be considered as equal to 0.35 kU/L). This conservative approach will ensure that changes from Baseline are consistent.

The following conventions will be used when presenting summary statistics for categorical study data:

- Categorical data will be summarized in terms of the number of subjects or observations providing non-missing data at the relevant time point (n), frequency counts and percentages. Any planned collapsing of categories will be detailed in the SAP text and the data displays.
- Percentages will be rounded to one decimal place. Percentages will not be presented for zero counts. Percentages will be calculated using number of subjects in each treatment group as the denominator. If sample sizes are small, the data displays will show the percentages, but any textual report must describe the frequencies.
- Change from Baseline will be summarized using shift tables where appropriate.

The following conventions will be considered regarding p-values:

- P-values greater than or equal to 0.001, in general, will be presented to three decimal places. P-values less than 0.001 will be presented as "<0.001".

Unless otherwise specified, summaries will be presented overall and by treatment group (Placebo / DBV712 250µg).

Titles for tables and listings produced will specify the type of data reported as well as the analysis set concerned (in parentheses).

Listings will generally include variables e.g.: subject identifier, sex and age, treatment group...

Unless otherwise specified, complete dates will be reported in listings using a DDMMYYYY format (i.e.: 01JAN2015) and time using a 24h clock-time (i.e.: 20:35).

Partial dates will be reported as MMMYYYY or YYYY.

Unless otherwise specified, all report outputs will be produced using SAS® version 9.4 or a later version in a secure and validated environment. Each report output will be provided in a Microsoft Word document (one document per output). All report outputs will be also pooled in one single PDF document with bookmarks and a comprehensive table of contents.

CONFIDENTIEL / Ne pas diffuser sans autorisation de DBV

CONFIDENTIAL / Do not distribute without DBV authorization

	Statistical Analysis Plan	
	EPITOPE (V712-304) – Statistical Analysis Plan	
	Référence du Document /Document Reference : CCI	Page : 19 / 74

CCI

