### **8.2 General Considerations**

#### **8.2.1 Statistical Methods**

The statistical analyses for the entire study as further outlined in the SAP will be included in the Clinical Study Report (CSR) for this protocol. The SAP will give a detailed description of the summaries and analyses (primary and secondary) that will be performed and clearly describe when these analyses will take place. The SAP will be prepared after the final protocol and finalized well ahead of the database lock to ensure the integrity of the statistical analysis and study conclusions.

All pre-defined statistical analyses will be performed after the database is released for unblinding. Statistical analyses will be performed using SAS® Version 9.3 or higher (SAS Institute, Cary, NC, USA).

Categorical variables will be summarized using number of observations and percentages. The denominator for percentages will be the number of subjects in the population with data available unless otherwise stated. Continuous variables will be summarized using descriptive statistics (number of observations [n], mean, standard deviation, minimum, first quartile [Q1], median, third quartile [Q3], and maximum).

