### **8.6.3 Vital Signs**

Observed vital sign values and changes from baseline will be descriptively summarized by visit and treatment group. All vital signs data will be listed.

The analysis of vital signs will focus on the incidence of clinically relevant abnormalities. The number of subjects evaluated and the number and percentage of subjects with clinically relevant post-baseline abnormalities at each visit will be presented. The criteria for clinically relevant post-baseline abnormalities are shown in Table 5.

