**Table 7 - Patch Application Site Skin Reaction Grading (Investigator)**

Skin Reaction	Grade if localized under the patch	Grade if extending beyond the patch	Grade regardless of localization
Negative	Grade 0	Grade 0	Grade 0
Only erythema, or erythema and infiltration	Grade 1A	Grade 1B	Grade 1
Erythema and few papules	Grade 2A	Grade 2B	Grade 2
Erythema and many or spreading papules	Grade 3A	Grade 3B	Grade 3
Erythema and vesicles	Grade 4A	Grade 4B	Grade 4

Grade 4B is considered as the most severe leading to 4B > 4A > 3B > 3A > 2B > 2A > 1B > 1A > 0.

The number and percentage of subjects with each grade will be presented by visit (and timepoint within visit for visit 4), both overall and by location of site reaction (under the patch / beyond the patch) by treatment group on the FAS.

Additionally, the worst grading overall (during the course of the trial) will be summarized as the number and percentage of subjects in each category on the Safety Set.

Patch site skin reaction data will also be listed on the Safety Set.

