#### 5.5.5 Vital Signs

The following vital signs will be recorded, before each DBPCFC and at any scheduled and unscheduled visits:

- Systolic blood pressure (in mmHg),
- Diastolic blood pressure (in mmHg),
- Heart rate (beats/minute),
- Respiratory rate (breaths per minute).

The following results will be tabulated for all vital signs:

- Summary statistics of values by visit and changes from Baseline
- Changes from Baseline by visit
- Number and percentage of subjects with vital signs abnormalities by post-baseline visit for heart rate, systolic blood pressure and diastolic blood pressure classified using the criteria defined in Table 8.

	Statistical Analysis Plan	
	EPITOPE (V712-304) – Statistical Analysis Plan	
	Référence du Document /Document Reference : CCI	Page : 58 / 74

CCI

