### 5.6.2 Symptomatic Reactions during DBPCFC

The objective symptoms collected during the DBPCFC are the following:

- Skin:
  - Erythematous rash (and % of rash area concerned)
  - Pruritus
  - Urticaria/ angioedema
  - Rash
- Upper respiratory:
  - Sneezing/ itching
  - Nasal congestion
  - Rhinorrhea
  - Laryngeal
- Lower respiratory:
  - Wheezing
- Gastrointestinal:
  - Diarrhea
  - Vomiting
  - Cardiovascular
- Eyes:

CONFIDENTIEL / Ne pas diffuser sans autorisation de DBV

CONFIDENTIAL / Do not distribute without DBV authorization

	Statistical Analysis Plan	
	EPITOPE (V712-304) – Statistical Analysis Plan	
	Référence du Document /Document Reference : CCI	Page : 60 / 74

CCI

- Conjunctivitis
- Any other objective symptoms (not reported, mild, moderate, severe)

The subjective symptoms collected are:

- Itchy mouth
- Itchy throat
- Nausea
- Abdominal pain
- Any other subjective symptoms (not reported, mild, moderate, severe).

With the exception of erythematous rash (recorded as Yes/No), each symptom is graded as: 0=" absent", 1=" mild", 2=" moderate" or 3=" severe". For erythematous rash, the % area involved is collected. The grading corresponding to the area involved is captured in the grading of the "Rash" symptom. No further step is required.

A total symptom score for each subject will be calculated as the sum of all severity score for all objective symptoms (for the Peanut formula only, excluding erythematous rash) and abdominal pain subjective symptom (only when grade is 2 or 3). This will be based on the sum of each of the following symptom being graded for severity as 0, 1, 2 or 3 (respectively absent, mild, moderate and severe):

Pruritus, Urticaria/ angioedema, Rash, Sneezing/ itching, Nasal congestion, Rhinorrhea, Laryngeal, Wheezing, Diarrhea, Vomiting, Cardiovascular, Conjunctivitis, Abdominal pain, Any other objective symptoms (one score for each of the other objective symptoms, 0 if no other objective symptom is recorded or if the answer to the question "Did the subject experienced any objective symptoms" is "No").

The reactions appearing during a DBPCFC will be summarized by group and by formula (peanut, placebo) for the enrolled set, showing:

- The number and percentage of subjects with objective symptoms (by severity) at Baseline and at Month 12 (actual value) (overall and by type of symptom)

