- The number and percentage of subjects with subjective symptoms (by severity) at Baseline and at Month 12 (overall and by type of symptom)
- Summary statistics on the Total symptom score at Baseline, at Month 12 (actual value) and the change from Baseline to Month 12 (using observed values).
- Symptoms used to calculate the Total symptom score will also be described using the number and percentage of subjects with symptoms by maximum severity at Baseline and at Month 12 overall and at each dose of DBPCFC. The Month 12 maximum symptom severity in the selected active DBV712 group (250 µg) compared to the placebo group will be analyzed on the FAS set excluding subjects with intercurrent events 1, 2 or 5 using a Cochran-Armitage Trend Test.

CONFIDENTIEL / Ne pas diffuser sans autorisation de DBV

CONFIDENTIAL / Do not distribute without DBV authorization

	Statistical Analysis Plan	
	EPITOPE (V712-304) – Statistical Analysis Plan	
	Référence du Document /Document Reference : CCI	Page : 61 / 74

CCI

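### SAP 5.1 takes percentages over the whole arm, where the protocol takes them over subjects with data; by-visit and by-challenge safety percentages are diluted as a result, and the change is not declared

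*SAP*

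**What the plan says.** The protocol's default (8.2.1) is: "The denominator for percentages will be the number of subjects in the population with data available unless otherwise stated". For vital signs, protocol 8.6.3 adds that the number examined should appear: "The number of subjects evaluated and the number and percentage of subjects with clinically relevant post-baseline abnormalities at each visit will be presented".

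SAP 5.1 first says that categorical data are summarised by the "number of subjects or observations providing non-missing data at the relevant time point (n), frequency counts and percentages". Its next bullet then fixes the denominator without any qualifier: "Percentages will be calculated using number of subjects in each treatment group as the denominator".

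Three displays inherit that rule because they name no denominator:

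- Investigator skin grades (SAP 5.5.3): "The number and percentage of subjects with each grade will be presented by visit". This table is on the FAS, meaning all randomized children.
- Vital signs (SAP 5.5.5): "Number and percentage of subjects with vital signs abnormalities by post-baseline visit for heart rate, systolic blood pressure and diastolic blood pressure". The protocol's request for the number evaluated is not repeated here.
- Challenge symptoms (SAP 5.6.2): "Symptoms used to calculate the Total symptom score will also be described using the number and percentage of subjects with symptoms by maximum severity". These are shown at baseline and Month 12, by group and formula, on the enrolled set.

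SAP 5.2.4 and 5.5 leave safety findings unimputed, apart from conventions for detection limits and partial or missing adverse-event fields. SAP 5.11, which lists departures from the protocol's analyses, does not mention the denominator.

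**The concern.** A child who has left the study, or missed a visit or a challenge, has no skin grade, blood pressure or symptom score at that time point. Under the SAP rule the child still counts in the denominator and can never count in a numerator. The reported figure is then no longer the rate among children examined. It falls as attendance falls, even if nothing changes in the children seen.

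Two comparisons could be distorted. Over time within an arm, a constant rate would appear to decline between early and late visits. For challenge symptoms this matters because change in severity from baseline to Month 12 is a listed safety criterion, and a positive baseline challenge was required for entry. Between arms, unequal attendance alone would produce a difference.

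**Working it through.** **Inputs from the documents.** Part B arm sizes of 233 active and 117 placebo, and a maximum drop-out of 15% (protocol synopsis, Number of Subjects, Part B). The documents give no figure for the effect of the denominator rule, so there is none to reproduce on this point. The sample size that supplies these inputs does reproduce: the exact probability that the Newcombe 95% lower bound is at least 15%, at 40% against 10%, is 0.908 with 233 and 117, against the stated 90% or more.

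**Assumed inputs.** Rates among assessed children of 20% and 50%, and an unequal split of missingness of 15% against 5%. None of these is in the documents.

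**Formula.** Reported % = rate among assessed × (number assessed ÷ number in arm). Under the protocol rule the second factor is absent, so a 20% rate is reported as 20% whatever is missing.

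**Numbers assessed.**

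- 15% missing: 233 × 0.85 ≈ 198; 117 × 0.85 ≈ 99.
- 5% missing: 233 × 0.95 ≈ 221; 117 × 0.95 ≈ 111.

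**Results under the SAP rule.**

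| Missing, active / placebo | True rate, both arms | Active reported | Placebo reported | Difference |
|---|---|---|---|---|
| 15% / 15% | 20% | 20 × 198/233 = 17.0% | 20 × 99/117 = 16.9% | +0.1 |
| 15% / 15% | 50% | 50 × 198/233 = 42.5% | 50 × 99/117 = 42.3% | +0.2 |
| 15% / 5% | 20% | 17.0% | 20 × 111/117 = 19.0% | −2.0 |
| 15% / 5% | 50% | 42.5% | 50 × 111/117 = 47.4% | −4.9 |
| 5% / 15% | 20% | 20 × 221/233 = 19.0% | 16.9% | +2.0 |
| 5% / 15% | 50% | 50 × 221/233 = 47.4% | 42.3% | +5.1 |

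The differences come from unrounded percentages. The 0.1 and 0.2 in the first two rows arise only from rounding the head counts.

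With equal missingness the rule understates both arms by the same 15% in relative terms. With unequal missingness it creates a difference whose sign depends only on which arm has more missing.

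**Which displays the rule reaches.** It does not reach displays that set their own base or are imputed:

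- the responder and CRD-threshold percentages, which use the primary analysis imputation (SAP 5.4.3.1);
- diary proportions, taken over days with a patch applied, and diary severity where it is shown among subjects with at least one reaction (SAP 5.5.3);
- the physical examination, which has a not-done category (SAP 5.5.6).

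For TEAE incidence over the whole study, the full arm is the proper denominator anyway.

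**Challenge symptoms.** The base here is unclear for a second reason. SAP 4.1 defines the enrolled set by signed consent, so it includes screen failures, who belong to no treatment group. The Month 12 severity trend test in the same section uses the FAS without intercurrent events 1, 2 and 5, so the table and its test do not share a base as written.

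**The case against.** The best defence is that there is no conflict. The protocol's rule holds only unless otherwise stated, and the protocol leaves detailed methods to the SAP. SAP 5.1 shows the non-missing n one bullet earlier, so the denominator sentence might mean only that percentages are taken within each arm's column. SAP 5.2.4 also says that observed data are used for safety. This reading is possible but strained. SAP 5.1 defines the non-missing n in its own words and then names something else as the denominator. The protocol's proviso permits exceptions, but it does not explain an unlisted replacement of the default.

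Other parts of the defence stand and limit the point:

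- A reader might infer that unassessed children are counted as free of reactions. The documents do not support that for skin grades. Grade 0 is its own row and an unassessed child does not enter it; all grades shrink and the rows fail to sum to 100%.
- A reader might infer that the rule favours the active arm. The documents give no drop-out by arm, and reversing the assumed split reverses the sign. Protocol 3.4 reports that local reactions led to discontinuation in 1.2% of an earlier study in older children. Missingness of that size would turn 20% into 20 × 0.988 = 19.8%.
- A reader might take the trend test's exclusions as a sign of error. They are correct, because a child without a challenge has no severity to rank. Only the accompanying table needs a matching base.
- The displayed n lets a careful reader recompute the percentage.
- Worst grade over the trial, maximum diary severity, TEAEs and local AESIs do not depend on attendance at any one visit.

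**Conclusion.** The SAP's denominator rule departs from the protocol and the departure is undeclared. Applied as written, it dilutes the by-visit skin grades, by-visit vital-sign abnormalities and Month 12 challenge symptoms by the share not assessed. At the 15% planning maximum the factor is 0.85, so an assumed 20% becomes 17%. A 15% against 5% split would create a spurious difference of about 2 points at a 20% rate and 5 points at a 50% rate, in either direction. Only the 15% is the protocol's, and it is a planning maximum rather than a forecast.

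The consequence is limited to descriptive safety tables. The stronger conclusion, that every percentage in the report is wrong or that the efficacy result is at risk, does not follow: the primary and secondary analyses have their own imputation rules and do not use this denominator. Nor is the assessed-only rate free of bias. If children leave because of patch reactions, those children drop out of that rate too. That is why the number not assessed must be visible.

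**What to change.** In SAP 5.1, state that for displays by visit or by challenge the denominator is the number of subjects with a non-missing assessment at that time point, and add a not-assessed count by arm to each such table. Keep the full arm as the denominator for whole-study incidence, disposition and imputed responder endpoints. In SAP 5.5.5, restore the number evaluated that protocol 8.6.3 asks for. In SAP 5.6.2, define the base for challenge symptoms as randomized children with a challenge at that time point; at Month 12 this also brings the table into line with the trend test.

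If the sponsor prefers the full-arm denominator, the alternative is to list it with a reason in SAP 5.11 and still show the not-assessed row.

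The cost is a few sentences in the SAP and a denominator change in the table programs. No extra data are needed. Some reported safety percentages will rise slightly.

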## 5.2 Statistical and Analytical Strategy

### 5.2.1 Statistical Testing Strategy

The primary measure of treatment effect will be the difference in response rates at Month 12 between active and placebo treatment groups. The primary analysis will be based on the 2-sided Farrington-Manning 95% confidence interval (CI) for the difference in response rates.

